## 10 INTERVENTION DISCONTINUATION

There are no formal criteria for discontinuing the study, although the discovery of any unanticipated adverse event would warrant immediate consideration of this.

Study participation for patient participants is anticipated to last no longer than a day, and in most cases approximately 15-30 minutes. Subjects may withdraw voluntarily from

participation in the study at any time and for any reason. Subjects who withdraw from the study will not be replaced. For any subject who withdraws from the study due to an AE or SAE, every effort will be made to collect safety data related to the AE or SAE and ensure the study receives appropriate care under medical supervision until the symptoms of any AE resolve or the subject's condition becomes stable.

## 11 STATISTICAL CONSIDERATIONS

### 11.1 General Design Issues

This is a pilot randomized controlled trial assessing the effect of a brief behavioral nudging intervention on surgeons' postoperative opioid prescribing. In addition to determining feasibility and acceptability, we are chiefly interested in obtaining precise estimates of mean and variance to aid in planning a larger, sufficiently powered efficacy trial.

Exploratory hypotheses include that (1) surgeons in the Intervention Arm will exhibit a larger pre-post percentage change in procedure-specific prescription size (measured by oral morphine equivalents [OMEs]) compared with surgeons in the Control Arm who do not receive the nudging intervention and (2) there will be no pre-post difference between the Intervention and Control Arms in terms of patient opioid consumption, opioid refills, medical visits for pain, satisfaction with analgesia, and opioid misuse.

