## **1.5 Sample Size and Population**

**Patients (initial phase):** We anticipate successfully contacting 5 patients per day for a total of 300 patients.

**Surgeons:** We anticipate obtaining mean pre-post prescribing change in up to 60 surgeons (30 per group).

**Patients (second phase):** We anticipate successfully contacting 5 patients per day for a total of 300 patients.

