## 5 STUDY DESIGN

We plan a pilot randomized controlled trial randomizing surgeons to either intervention (direct feedback) or control (no direct feedback) arms. Surgeons frequently performing specific elective general, gynecologic, orthopedic, and neurological surgeries at VUMC will be identified during a 30-day study lead-in period. Then, patients aged at least 18 years undergoing these surgeries at VUMC during study days 1-60 will be contacted by telephone 14 days postoperatively (study days 15-74) and asked to perform an opioid pill count; they will also be asked about opioid refills, satisfaction with analgesia, emergency room visits or hospitalizations for pain, and opioid misuse. The electronic medical record will be also queried for the size of the initial postoperative opioid prescription as well as evidence of any refills for each enrolled subject. We anticipate successfully contacting 5 patients per day for a total of 300 patients in this initial phase. We plan to consent patients electronically at the time of the telephone contact as consenting patients immediately after surgery may influence their subsequent opioid consumption.

Surgeons will be consented without overt discussion of the nudge intervention. Following the first block of surgeries and associated patient follow-up (study days 1-74), data will be analyzed and then surgeons will be randomized in a 1:1 ratio to the intervention or control arms. Randomization will be stratified by both surgical specialty and by mean opioid prescription size during the initial block of surgeries. After study day 97, surgeons in the intervention arm will be provided procedure-specific direct feedback on opioid prescribing and consumption for their patients who had surgery during days 1-60.

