After this intervention, we will assess pre-post change in opioid prescription size (measured in oral morphine equivalents) from baseline between the two groups for surgeries performed during days 108-167. That is, mean size of post-intervention prescriptions (from electronic medical record queries) will be compared with mean pre-intervention prescription size by the same surgeon for the same procedure in order to calculate change from baseline. Primary outcomes are measures of study feasibility and acceptability given that this is a pilot study. The main exploratory outcome will be mean percentage change in procedure-specific prescription size. We will then compare mean per-surgeon percentage change in prescription size between the direct feedback and no-direct-feedback groups. Multiple regression analyses adjusting for case type and surgical specialty will also be employed to permit more granular examination of the targeted changes. To evaluate other exploratory outcomes, we will contact patients undergoing post-intervention surgeries (during days 108-167) 14 days postoperatively (days 122-181) to assess pre-post changes in patient opioid consumption, satisfaction with analgesia, medical visits for pain, opioid refills, and opioid misuse. We again anticipate contacting 5 patients per day for a total of 300 patients in this second phase.

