## 9 SAFETY ASSESSMENTS

### 9.1 Risk/Benefit Profile and Risk Mitigation

Potential risks: We anticipate that this will be a minimal risk study. There is a small risk that people who are not connected with this study will learn a participant’s identity or their personal information through violation of HIPAA compliance and established research protocols. There is also a small risk that physicians may experience some discomfort in learning the opioid consumption patterns of their patients, or that deception was used in the initial vague description of the purpose of the study. Finally, there is a small risk that surgeon participants in the Intervention Arm may, following the intervention, prescribe insufficient amounts of postoperative opioids and consequently that patients undergoing surgery with these physicians after the intervention may be at higher risk of pain-related medical visits.

Potential benefits: There may be no direct benefits to patients participating in this study. Providers may benefit from the post-surgical opioid prescribing guidelines disseminated during the intervention. Prescribers may also be more likely to exercise more careful use of opioids after they have been made aware of discrepancies between opioids prescribed and consumed. They may also be more likely to adjust their prescribing practices, discuss opioid prescribing with colleagues, and identify careful use of opioids with their self-image in the future.

Risk mitigation: Study staff will protect the privacy of study participants. We do not

anticipate greater than minimal risk to patients or surgeons given that patient contact consists only of a pill count and several questions related to postoperative pain and the surgeon contact consists only of feedback regarding opioid prescription/consumption ratio and published prescribing guidelines. Differences in pain-related medical visits will be evaluated as described below. The consent process informs a volunteer about the study, indicates the participation is voluntary and he/she has the right to stop at any time. Risks are described during the consent process. Surgeons will be fully debriefed on the purpose of the study as soon as deception is no longer necessary (upon completion of the study).

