### 11.2 Sample Size and Randomization

We anticipate obtaining mean pre-post prescribing change in up to 60 surgeons (30 per group). This exceeds the suggested rule-of-thumb threshold of 12 per group for an adequately precise estimate of the variance of a continuous variable to use in future studies.(16)

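### Exploratory hypothesis 2 predicts no difference between arms in patient outcomes, but the plan has no margin, precision target or clustered analysis that could support it

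*Combined protocol and SAP*

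**What the plan says.** Section 11.1 introduces two predictions with the words "Exploratory hypotheses include that". The first is that intervention surgeons will show a larger percentage change in prescription size. The second is that "there will be no pre-post difference between the Intervention and Control Arms in terms of patient opioid consumption", and likewise in opioid refills, medical visits for pain, satisfaction with analgesia and opioid misuse. The same section says the pilot's chief interest beyond feasibility and acceptability is in estimates of mean and variance "to aid in planning a larger, sufficiently powered efficacy trial".

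Sections 1.2 and 3.2 treat the same patient outcomes neutrally: the aim there is to find out whether the nudge affects them.

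On size, section 1.5 says of each phase "We anticipate successfully contacting 5 patients per day for a total of 300 patients". Section 11.2 expects up to 60 surgeons, 30 per group, and justifies this by a rule of thumb of 12 per group for estimating the variance of a continuous variable. It does not mention the patient outcomes. Section 11.4.1 sets a goal of more than 50% agreement among patients contacted.

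On analysis, section 11.5 says only that pre-post changes in the patient outcomes will be assessed across groups. Surgeons are the randomized unit (section 5: "surgeons will be randomized in a 1:1 ratio to the intervention or control arms"), but no model, interval or allowance for patients clustered within surgeons is described. Section 9.1 acknowledges that "patients undergoing surgery with these physicians after the intervention may be at higher risk of pain-related medical visits", and section 9.2 plans monitoring of pain visits by arm without a formal safety analysis.

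**The concern.** A prediction of no difference can be supported only by an interval narrow enough to rule out differences that matter. That requires either a margin fixed in advance or, at least, an interval reported and read for what it leaves open. Hypothesis 2 has neither. When a study is imprecise, a non-significant result is the likely outcome whether or not harm exists, and a hypothesis worded this way invites that result to be written up as confirmation.

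Pain visits are where this matters most, because section 9.1 names them as a possible patient harm of reduced prescribing. A pilot report stating that the no-difference hypothesis was supported could be carried into the planning of the larger trial as reassurance that these data do not provide.

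**Working it through.** **Inputs from the documents**
- Patients per phase: 5 per day × 60 days = 300, which reproduces the stated figure (sections 1.5 and 5).
- Surgeons: up to 60, 30 per group (section 11.2), so 300 / 60 = 5 patients per surgeon per phase.
- Agreement goal: more than 50% of patients contacted (section 11.4.1).

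**Assumptions, because the documents give no figure**
- An even split gives 300 / 2 = 150 patients per arm and phase. If the 300 are contacts and half agree, this becomes 75.
- Pain-visit rate p: 5% or 10%.
- Two-sided 95% intervals. The two phases hold different patients and are treated as independent. No clustering unless stated.

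**Step 1. Interval width for the contrast that hypothesis 2 names.** The contrast is (change in the intervention arm) − (change in the control arm). It is built from four proportions, so with the same p in each:

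half-width = 1.96 × √(4p(1 − p)/n)

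| p | n per arm and phase | Calculation | Half-width (points) | Doubling (points) | Excluded at observed zero difference? |
|---|---|---|---|---|---|
| 5% | 150 | 1.96 × √(0.19/150) | 7.0 | 5 | no |
| 5% | 75 | 1.96 × √(0.19/75) | 9.9 | 5 | no |
| 10% | 150 | 1.96 × √(0.36/150) | 9.6 | 10 | yes, narrowly |
| 10% | 75 | 1.96 × √(0.36/75) | 13.6 | 10 | no |

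**Step 2. Chance that a true doubling is non-significant.** Let the intervention arm's follow-up rate be 2p and the other three rates p.

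SE = √([3p(1 − p) + 2p(1 − 2p)]/n), and the chance of significance is approximately Φ(p/SE − 1.96).

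- 5% to 10%, n = 150: SE = √((0.1425 + 0.09)/150) = 0.0394; 0.05/0.0394 = 1.27; non-significant about 75% of the time.
- 5% to 10%, n = 75: SE = 0.0557; ratio 0.90; about 85%.
- 10% to 20%, n = 150: SE = √((0.27 + 0.16)/150) = 0.0535; ratio 1.87; about 54%.
- 10% to 20%, n = 75: SE = 0.0757; ratio 1.32; about 74%.

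Simulation agrees to within about one percentage point.

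**Step 3. Sensitivity to clustering.** With an assumed intraclass correlation of 0.05 and 5 patients per surgeon, the design effect is 1 + 4 × 0.05 = 1.2. At n = 150 the half-widths become 7.0 × √1.2 = 7.6 and 9.6 × √1.2 = 10.5 points. The narrow exclusion at 10% is then lost. This calculation gives no credit for the same surgeons appearing in both phases, so it may overstate the loss.

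**Step 4. Sensitivity to scale and rate.** For a ratio of risk ratios at an observed value of 1, the upper 95% limit is exp(1.96 × √(4(1 − p)/(np))). With n = 150 and no clustering it is 4.04 at 5%, 2.61 at 10% and 1.90 at 20%, and it falls below 2 at a rate of about 17.6%. So whether a doubling is excluded depends on the visit rate, the scale and the number of patients. At 20%, with no true effect, the chance of excluding a doubling is only about 56%.

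**The case against.** The strongest reply is that nothing in the plan commits the trial to the feared error. No section sets a test, a significance level or a rule that a non-significant result supports hypothesis 2. The hypothesis is labelled exploratory, the primary outcomes are descriptive, and a larger powered trial is the stated purpose. All of this stands and is why the point is minor. It leaves the gap in place: the hypothesis is worded as a null, and nothing says how a null-looking result is to be read.

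A second reply is that patient safety does not rest on this hypothesis. Section 9.3 plans electronic record review of follow-up patients at about postoperative day 14 with chart review of cases, section 9.2 has pain visits monitored by arm, and sections 9.3.1 and 9.4 provide quarterly reports to the DSMB. This also stands, and the record review could give a larger follow-up denominator than the consenting patients. No matching baseline review is described, however, and the any-surgery cohort in section 6.3 covers intervention surgeons only, so neither source supplies the pre-post contrast between arms.

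Several stronger readings are tempting and should be resisted:
- A reader might infer that the design cannot exclude a doubling of pain visits at all. No visit rate is given, and at 10% with 150 per arm and phase a 10-point rise is narrowly excluded without clustering.
- A reader might infer that any realistic harm would go undetected. A rise from 5% to 15% with 150 per arm and phase (SE 0.042) would be significant about 65% of the time.
- A reader might take pain visits to be the main patient risk. Section 9.1 lists them last and calls the risk small.
- A reader might extend the doubling argument to refills, consumption, satisfaction or misuse. The calculation covers pain visits only.

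**Conclusion.** The point holds in a limited form. Hypothesis 2 predicts no difference, yet the plan contains no margin, precision target or clustered analysis that could support that prediction, and the only sample-size rationale concerns a different quantity. Section 11.1 is also out of line with sections 1.2 and 3.2, which ask the question neutrally.

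For pain visits the imprecision is material at an assumed 5% rate, where a doubling is not excluded at either sample size and would usually be missed. At an assumed 10% rate the answer turns on whether 150 or 75 patients per arm and phase contribute, and on clustering. These results rest on assumed rates, an even split between arms, and independence of patients except where a design effect is shown. The 150 is probably a ceiling, since 60 surgeons is an upper limit and section 6.2 bars those with fewer than 3 cases from randomization. The 75 is the floor implied by the agreement goal if the 300 are contacts and not consents.

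Severity is minor: one sentence in an exploratory section of a pilot, with no effect on the primary outcomes.

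**What to change.** In section 11.1, replace hypothesis 2 with an estimation aim that matches sections 1.2 and 3.2, and carry it into section 11.5. For example: for each patient outcome, the difference between arms in pre-post change will be estimated with a 95% confidence interval that accounts for clustering of patients within surgeons; for pain visits, the largest increase that the interval does not exclude will be stated; and a non-significant difference will not be reported as no difference.

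No margin, additional patients or new procedures are needed. The cost is one or two sentences of text and a clustered interval in the analysis. The downside is that the pilot gives up a no-difference conclusion on these outcomes, which the present plan has no means of supporting.

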### 11.2 Sample Size and Randomization

We anticipate obtaining mean pre-post prescribing change in up to 60 surgeons (30 per group). This exceeds the suggested rule-of-thumb threshold of 12 per group for an adequately precise estimate of the variance of a continuous variable to use in future studies.(16)

#### 11.2.1 Treatment Assignment Procedures

For randomization, a list of all surgeon participants will be generated. Using random.org's sequence generator, a true random integer sequence derived from atmospheric noise will determine order in the list. Randomization will be stratified by surgical specialty (e.g., neurological surgery) and by mean opioid prescribing amount during the first 60-day surgical period prior to randomization (greater or equal to median vs. below median). We will at minimum ensure an even or near-even split among the four overall major surgical divisions (general, orthopedic, gynecologic, and neurological) across the intervention and control arms.

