### 6.3 Study Enrollment Procedures

During the 30-day lead-in period, study *surgeon* participants will be identified through VUMC EMR queries of historical and booked case numbers for the specific procedures listed in section 4.1, above. Given the nature of the planned behavioral nudging intervention, it is not feasible for full consent to be obtained prospectively from surgeon participants as this would very likely affect prescribing behavior in both the Intervention and Control Arms due to the Hawthorne effect. Consequently, we plan to request permission from the VUMC Institutional Review Board to utilize deception for *surgeon* participants, who will be asked to consent for participation in a study giving them information about their patients' opioid consumption (surgeons will be debriefed fully on study purposes upon completion of the study). Surgeon participants will be prospectively selected in a participant log kept by study staff. Surgeons will be randomized on a 1:1 basis to either the Intervention or Control Arms prior to administration of the nudge intervention. Enrolled surgeons must complete a minimum 3 listed cases during the initial 60-day study period (study days #1-60) to be eligible for randomization.

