### 11.4.2 Exploratory outcomes

- Mean pre-post percentage change in procedure-specific prescription size, as measured by OMEs. Mean size of post-intervention prescriptions (from electronic medical record queries) will be compared with mean pre-intervention prescription size by the same surgeon for the same procedure in order to calculate change from baseline.
- Pre-post change in patient opioid consumption, as measured by OMEs
- Pre-post change in satisfaction with overall postoperative analgesia, as measured by patient-reported numeric rating scale
- Pre-post change in patient satisfaction with general amount of opioids prescribed
- Pre-post change in incidence of medical visits for pain (office visits, emergency department visits, and/or hospital admissions)
- Pre-post change in number of subsequent opioid refills after the initial postoperative prescription (from EMR/PDMP data)
- Surgeon-reported perceived usefulness of intervention (goal: median response to question “Do you think the nudge intervention would be useful?”  $\geq 4$  on 0-5 scale, where 0 is “not at all” and 5 “extremely.”)

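### Section 11.2.1 does not say whose median separates high from low prescribers; a within-specialty median would balance prescribing level somewhat better than one overall median

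*Combined protocol and SAP*

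**What the plan says.** Section 5 names the two factors without a cut-point: "Randomization will be stratified by both surgical specialty and by mean opioid prescription size during the initial block of surgeries". Section 11.2.1 adds the cut for the second factor, "by mean opioid prescribing amount during the first 60-day surgical period prior to randomization (greater or equal to median vs. below median", and describes a single list of participating surgeons put into random order. Neither section says which surgeons the median refers to, or that the mean is adjusted for the operations performed. The only balance that 11.2.1 promises outright is by division: "We will at minimum ensure an even or near-even split among the four overall major surgical divisions".

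The main exploratory outcome is on a different scale: "Mean pre-post percentage change in procedure-specific prescription size, as measured by OMEs", with each surgeon compared with their own baseline for the same operation (sections 11.4.2 and 11.5). The regression planned in 11.5 adjusts for case type and specialty; baseline prescribing level is not listed.

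**The concern.** The outcome compares prescriptions only within a procedure, whereas the stratification factor pools a surgeon's prescriptions over all listed procedures. Section 6.1 lists operations from perineorrhaphy to total knee arthroplasty. A pooled mean therefore reflects which operations a surgeon does as well as how generously that surgeon prescribes. If it is cut at one overall median and specialties differ in typical size, surgeons of one specialty tend to fall on the same side. The factor then partly repeats specialty and does less to balance high and low prescribers who do similar work.

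Baseline level can matter through regression to the mean. Section 6.3 says "Enrolled surgeons must complete a minimum 3 listed cases during the initial 60-day study period", so a baseline mean may rest on very few prescriptions, and percentage change is measured from it. Because 11.5 does not adjust for baseline level, stratification is the only stated protection against an arm imbalance in it. Section 11.1 says that the pilot is meant to supply estimates of mean and variance for a larger trial.

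**Working it through.** **1. The plan's own figures.** Section 11.2: "We anticipate obtaining mean pre-post prescribing change in up to 60 surgeons (30 per group". 60 / 2 = 30 per arm, which reproduces the stated figure and exceeds the cited rule of thumb of 12. Two factors give 4 × 2 = 8 strata, or 60 / 8 = 7.5 surgeons per stratum on average. With 300 first-phase patients, 300 / 60 = 5 per surgeon on average, with a minimum of 3 listed cases. The plan has no power calculation to reproduce.

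**2. The missing input.** The overlap depends on the share of between-surgeon variance in mean prescription size that lies between specialties. The documents give no prescribing data, so this share is an assumption, varied here from 0 to 0.9.

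**3. Balance within a specialty.** Simulation, 3,000 runs per setting: 60 surgeons, 15 per specialty, equally spaced specialty means, normal variation within specialty, 1:1 allocation within each stratum. The measure is the SD of the chance arm difference in baseline within a specialty, in within-specialty SDs. Under specialty-only stratification it should be √(1/8 + 1/7) = 0.52, and the simulation gave 0.51-0.52. Variance removed = 1 − (SD / 0.52)².

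| Between-specialty share | Surgeons on their specialty's majority side of the overall median | SD, overall median | SD, within-specialty median | Variance removed, overall | Variance removed, within |
|---|---|---|---|---|---|
| 0 | 59% | 0.33 | 0.34 | 60% | 57% |
| 0.25 | 70% | 0.37 | 0.34 | 49% | 57% |
| 0.5 | 80% | 0.41 | 0.34 | 38% | 57% |
| 0.7 | 87% | 0.44 | 0.34 | 28% | 57% |
| 0.8 | 91% | 0.47 | 0.34 | 18% | 57% |
| 0.9 | 96% | 0.49 | 0.34 | 11% | 57% |

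With unequal specialties (20/15/18/7) the pattern is the same: SD 0.37 to 0.53 for the overall median, 0.38-0.39 for the within-specialty median and 0.56-0.57 for specialty alone.

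**4. Adding procedures and sparse cases.** Step 3 treats the baseline as one clean number. Simulations that add procedure differences and few cases per surgeon give smaller gains. Over a range of assumed values with 60 surgeons and differing specialties, the overall median removed 21-40% and the within-specialty median 28-50%. One specific setting (15/20/20/5 surgeons, 5 cases each, log SD 0.4 for habit and 0.5 for procedure within specialty) gave:
- overall median of raw means: 23-34%;
- within-specialty median of raw means: 36-37%;
- within-specialty median after dividing each prescription by its procedure mean: 51-52%.

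Where procedures do not differ, that division lost ground against the raw within-specialty median: 2-4 points in one set of runs and 5-12 in another.

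**5. Whole trial and precision.** In the step 3 runs, the SD of the whole-trial arm difference in baseline (total-SD units), overall versus within-specialty median, is 0.157 vs 0.155 at a share of 0.25, 0.129 vs 0.108 at 0.7, and 0.099 vs 0.083 at 0.9.

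For the outcome, let r be the within-specialty correlation of baseline with percentage change (assumed) and k the fraction of imbalance variance that remains. The variance of the arm difference is proportional to 1 − r² + r²k. A case favorable to the change assumes specialty sizes of 75/100/300/200 OME: the overall median removes 20-31% (k = 0.80 to 0.69) and the within-specialty median 61% (k = 0.39).
- r = 0.3: overall 0.91 + 0.09 × 0.80 = 0.982, or with 0.69, 0.972; within 0.91 + 0.09 × 0.39 = 0.945. Square roots of the ratios are 0.981 and 0.986, so the standard error falls by 1.4-1.9%.
- r = 0.5: overall 0.950 or 0.9225; within 0.8475. The standard error falls by about 4-5.5%.

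**The case against.** The text does not say that the median is an overall one. In a sentence that also stratifies by specialty, a within-specialty median is possible, and under that reading the loss of balance from an overall cut disappears. All the magnitudes rest on assumed prescribing levels. The stated scheme is not shown to do harm: in every setting of step 3 it balances at least as well as specialty alone, and at a low between-specialty share it nearly matches the within-specialty median. The outcome is already measured against the surgeon's own procedure-specific baseline, and the primary outcomes are descriptive. Standardizing by procedure is also not free. With about 300 patients over a long list of operations, procedure means are sparse, and a surgeon who supplies every case of a procedure averages exactly 1 and contributes no information. These arguments stand, and they limit the point to a minor one. They do not remove it, because the single list of surgeons makes one overall median the plainest reading, and if a within-specialty median was meant, the same sentence still needs the same words.

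A reader might go further and infer that the factor merely duplicates specialty, leaves some strata almost empty and so fails to balance prescribing. The documents do not support that. It would need roughly 70% or more of the variance to lie between specialties, and they give no figure. A reader might also infer that prescribing habit relative to peers is the strongest predictor of percentage change. Nothing in the plan says so, and the feedback described in section 7.1 sets a surgeon's prescribing against that surgeon's own patients' consumption, with no peer comparison.

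**Conclusion.** The point holds as a minor one. The reference group of the median is unstated. If it is all surgeons, prescribing level within a specialty is balanced less well than it could be, to a degree that depends on how far specialties differ. On assumed values with 60 surgeons and differing specialties, the within-specialty cut removes about 28-50% of chance imbalance variance against 21-40%; with no specialty differences the two are about equal. The gain in precision for the exploratory comparison is small: a few percent of the standard error under favorable assumptions. Randomization is valid under either cut, and the feasibility and acceptability outcomes are untouched.

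**What to change.** In section 11.2.1, define the second factor as: mean baseline prescription size in OMEs, at or above versus below the median of randomized surgeons in the same specialty. Align section 5 with it. The cost is one sentence and a line of code, using baseline data that the schedule in section 8.1 has under review on days 75-93, when randomization takes place. A small specialty will have small strata (7 surgeons split 4 and 3), so 11.2.1 should also say how odd numbers are allocated.

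Optional: first divide each prescription by the all-surgeon baseline mean for its procedure, then average per surgeon. This helps where procedures within a specialty differ widely in size, and adds some noise where procedures are sparse or done by one surgeon. Adding baseline prescribing level to the regression in 11.5 would complement either choice at no data cost.
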